11.4. Subject Discontinuation Criteria

A premature discontinuation will occur when a subject who signed informed consent ceases participation in the study, regardless of circumstances, prior to the completion of the protocol. Subjects can be prematurely discontinued from the study for one of the following reasons:

- An adverse event (AE)
- A protocol violation (reason must be specified, for example: lack of compliance, use of a prohibited concomitant medication, failure to meet inclusion/exclusion criteria after study entry, etc)
- Withdrawal by subject (reason must be specified)
- The subject was “lost to follow-up”
- Other reasons (reason must be specified, for example: the subject moved, pregnancy, investigator decision, Sponsor decision to terminate trial, etc)

If a subject discontinues from the study, all end-of-study procedures should be conducted as detailed in Schedule of Events. The date a subject discontinues and the reason for discontinuation will be recorded in the source documentation and Electronic Case Report Form (eCRF). If, however, a subject withdraws consent, no end-of-study procedures are required except the collection of AE information. This information should be recorded in the source documentation and the eCRF.

11.4.1. Replacement Procedures

Subjects who discontinue prematurely from the study will not be replaced.

12. PROCEDURES AND TREATMENTS

12.1. Study Visits

The Schedule of Events to be performed at each visit is shown in section 5. Provided below are further details where additional instruction about the assessments that will be performed is deemed to be needed.

12.1.1. Subject Screening

Upon completion of Day 71 assessments in the double-blind study EN3835-201, a subject will be eligible to enter this open-label extension study. All potential subjects eligible for screening in EN3835-202 will be pre-populated in the electronic data capture (EDC) system. The status of all subjects (eg, screen fails) will also be kept in the EDC system.

12.1.2. Screening Assessments

After obtaining informed consent, the full assessment of eligibility will be conducted and prior to study entry, screening assessments will be performed. Details about how the informed consent will be obtained and documented are provided in section 21.3, Subject Information and Consent. The subject may be entered into the observational phase of the study and complete safety and cellulite severity assessments at 3-month intervals as detailed in Table 2. In addition, once the study blind is broken in study EN3835-201, enrolled subjects will be asked if they wish to receive additional open-label treatments. If a subject elects to receive open-label treatment, study assessments will be conducted in accordance with Table 3.

12.1.3. Study Entry/Observational Assessments

A subject who gives written informed consent and who satisfies all eligibility criteria (section 11) may be entered into the observational phase of the study and complete safety and cellulite severity assessments at 3-month intervals as detailed in Table 2. The first visit will be determined by the date of enrollment in study EN3835-202 relative to the Schedule of Events for study EN3835-202 (Table 2). For example, if a subject enrolls after the Day 90 visit window, the first observation visit for that subject would be Day 180. In addition, once the study drug blind is broken in study EN3835-201, enrolled subjects will be asked if they wish to receive additional open-label treatments. If a subject elects to receive open-label treatment, study assessments will be conducted in accordance with Table 3. The subject identification number will be carried over from the double-blind, placebo-controlled study (EN3835-201). All subjects must complete Screening A and at least 1 Observation visit before Screening B can occur. Once the study blind was broken, the EN3835-201 placebo subjects were allowed to directly proceed to Screening B.

12.1.3.1. Three-Month Assessments

Subjects will return within 20 days (± 4 days) of completion of the double-blind study for the first of 4 safety and cellulite severity evaluation visits. Assessments to be completed at these visits are detailed in Table 2. Subjects are to return at 3-month intervals until they have completed at least 12 months from Day 1 of the double-blind study. At these visits, the quadrant previously treated with EN3835 in the EN3835-201 study or quadrants treated with EN3835 in the

open-label study will be evaluated. If the quadrant treated in study EN3835-201 is retreated in the open-label study, the 3-month assessments will reset to treatment visit 1/Day 1 of the open-label treatment and the study visits will continue as described in [Table 3](#) followed by 3-month assessments as described in [Table 2](#). If a different quadrant is treated in the open-label study, the 3-month assessments of both the quadrant treated in the double-blind study (EN3835-201) and the quadrant treated in the open-label study will continue.

12.1.3.2. Durability Assessments

An assessment of treatment durability will include subjects treated with open label EN3835 in the current study as well as subjects that received active EN3835 in study EN3835-201 and showed a composite improvement of at least 1 level in the PR-PCSS and CR-PCSS. Similar to other EN3835-202 observational assessments, the first durability visit will be determined by the date of enrollment relative to the associated Schedule of Events. For subjects who were treated with active EN3835 in the double-blind study ([Table 4](#)), and who give written informed consent and meet all eligibility criteria, durability assessments of the quadrant treated in the double-blind study are to be conducted *in addition* to any assessments of the different quadrant treated in the open-label study. Subjects may complete assessments for durability of all treated quadrants (whether initiated in the double-blind and open-label study) at the same visits, where subject and site schedules permit.

12.1.4. Treatment Assessments (Optional)

After unblinding of treatment assignment in the EN3835-201 study, subjects are eligible for optional treatment in the open-label study, provided they meet the inclusion and exclusion criteria detailed in section [11](#) and at least 1 quadrant meets the criteria for treatment. A subject may receive a maximum of 2 courses of treatment (6 treatment sessions) overall (total of treatments in double-blind and open-label study). If a subject received placebo in the double-blind study, she may be eligible for 2 treatment courses in the open-label study; if a subject received active drug in the double-blind study, she may be eligible for 1 additional treatment course (3 treatment sessions) in the open-label study.

Selection of Treatment Quadrant

During the Screening B visit, each subject will have photographs taken of the 4 targeted quadrants of the study (eg, their left and right buttocks and left and right posterolateral thighs). Subjects will receive instructions ([Appendix D](#)) for using the PR-PCSS and will use the scale to rate the severity of their cellulite in each of the 4 quadrants by comparing each of their digital image photographs with the PR-PCSS instrument. This self-assessment will take place in a private setting to minimize any potential bias from site personnel. The Investigator will then assess each of the subject's 4 quadrants live in real-time using the CR-PCSS. The Investigator will then examine each of the 4 quadrants live to assess the subject using the Hexsel CSS as described in section [13.1.1.6.\(12\)](#) Subjects must have at least 1 quadrant that meets the following criteria for treatment in the study:

1. PR-PCSS score of 3 or 4, and
2. CR-PCSS score of 3 or 4, and
3. Hexsel CSS score no greater than 13.

After the independent assessments are completed separately by the subject and the Investigator, the Investigator will review his/her assessments and the subject's assessment to determine which quadrants, if any, are eligible. The eligible quadrants (must meet all 3 of the inclusion criteria (PR-PCSS, CR-PCSS, and Hexsel CSS scores), if any, for treatment will be determined by the Investigator after which the quadrant selected will be at the discretion of the subject. For subjects treated with EN3835 in the double-blind study, if the quadrant treated in the double-blind study (EN3835-201) has PR-PCSS and CR-PCSS ratings identical or more severe than the double-blind study (EN3835-201) PR-PCSS and CR-PCSS baseline ratings (Baseline is Day 1 of study EN3835-201), subjects can elect to have that same quadrant re-treated. Subjects who choose re-treatment of the previously treated quadrant will be classified in the re-treatment arm. If another quadrant besides the previously treated quadrant meets all 3 of the inclusion criteria, subjects can choose to be treated in the naive quadrant. Subjects who choose treatment into a naive quadrant will be classified in the re-dosing arm.

Assessments made with the PR-PCSS (from digital image), the CR-PCSS (live assessment), and the Hexsel CSS score during the open-label Screening B visit will be the baseline severity of EFP in the selected quadrant.

A subject who received placebo in the double-blind study may be treated in the same quadrant in the open-label study if the quadrant still meets all 3 criteria OR another qualifying quadrant may be selected for treatment by the subject. Following Day 71 of a treatment course (3 treatment sessions), subjects can choose to receive a second treatment session in either the same quadrant if it still meets qualification criteria or in a different quadrant that meets qualification criteria. For the first treatment course, these subjects will be considered in the treatment arm. For the second treatment course, if the same quadrant is treated, subjects will be in the re-treatment arm; if a different quadrant is treated, subjects will be considered in the re-dosing arm.

If no quadrant meets all 3 criteria, the subject may continue in the observation-only study with safety and cellulite severity evaluations performed at 3-month intervals but may not receive treatment in this study.

Selecting and Marking Dimples

Selection of dimples to be treated in the selected quadrant is at the discretion of the Investigator or qualified designee. Dimples must be well-defined and evident when the subject is standing in a consistent relaxed pose (without the use of any manipulation such as skin pinching or muscle contraction). Each subject will receive 3 treatment sessions of study drug in the selected quadrant. During each treatment session, the treatment quadrant will be photographed before and after dimple marking while the subject is standing in a consistent relaxed pose as described in the Photography Manual. The cellulite severity assessments using the PR-PCSS and CR-PCSS will be completed prior to dimple marking at treatment visits 2, 3, and 4/end of treatment.

12.1.4.1. Screening B (Days -14 to -1 Relative to Open-label Treatment Visit Day 1)

Subjects meeting the relevant criteria listed in section 11.2 may be eligible for treatment in the open-label study. The following procedures will be performed and documented during the screening period:

1. Evaluate eligibility based on inclusion/exclusion criteria (section 11.2)

2. Subject will have digital photographs taken of the 4 targeted quadrants of the study (left and right buttocks, and left and right posterolateral thighs) (section 13.1)
3. Subjects will get instruction on the use of the PR-PCSS (Appendix D)
4. Subjects will rate each quadrant using the PR-PCSS while viewing their digital images (section 13.1.1.1)
5. The Investigator will conduct independent live assessments of subject's cellulite severity of each quadrant using the CR-PCSS (section 13.1.1.4) after the subject completes her rating and with no knowledge of the subject's ratings of her quadrants.
6. The Investigator will conduct live cellulite evaluation of each quadrant using the Hexsel CSS (section 13.1.1.6).
7. If at least 1 quadrant qualifies based on PR-PCSS, CR-PCSS, and Hexsel CSS ratings, subject may return for treatment on treatment visit 1. If none of the 4 quadrants qualify, the subject may remain in the study and have safety and cellulite severity evaluations performed at 3-month intervals but is not eligible for treatment.
8. Subject will select an eligible quadrant (based on qualifying scores) to be treated at their discretion.
9. Medical history including EFP history. Medical history will be based on EN3835-201 eCRF; only updates to the history need to be captured at Screening B visit.
10. Record prior and concomitant medications/procedures. Prior medications will be based on EN3835-201 eCRF; only updates and concomitant medications need to be captured at Screening B visit (section 12.2).
11. Physical examination including measurement of body weight and height (section 14.10)
12. Vital sign measurements (section 14.8)
13. 12-lead electrocardiogram (ECG), not necessary if the date of the ECG obtained during the double-blind study (EN3835-201) is within 12 months of the date of the Screening B visit (section 14.9)
14. Collection of samples for:
 - a. Clinical laboratory testing (section 14.7)
 - b. Urine pregnancy testing (section 14.7)
15. Adverse events (section 14)

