EN3835-201 if subject was treated with EN3835. Each treatment session will consist of up to 12 injections (0.07 mg/0.3 mL per injection) of EN3835 for a dose of 0.84 mg and volume of 3.6 mL. Only a quadrant with moderate (rating of 3) or severe (rating 4) level of severity as assessed by the subject and investigator using the PR-PCSS and the CR-PCSS, respectively, will be eligible for treatment; if more than 1 eligible quadrant exists, the quadrant selected will be at the discretion of the subject. Treatments will be administered on Days 1, 22, and 43; subjects will be assessed for safety on Days 1, 22, 43, and 71 and for cellulite severity assessments at Screening visit and on Days 22, 43, and 71. After Day 71, they will be observed every 3 months in each treated quadrant (including both open-label and double-blind treated quadrants, if different quadrants were treated across both studies). Durability of open-label treatment with EN3835 will be assessed for up to 1 year (Day 360). Durability beyond Day 360 will be assessed in subjects who received active treatment in EN3835-201 and showed a composite improvement of at least 1 level on both the CR-PCSS and the PR-PCSS. In these subjects, the original quadrant treated in EN3835-201 will be assessed until the end of the current study, in addition to any treated quadrants occurring in the current study. Assessments of durability beyond Day 360 may also include subjects who opted not to receive additional treatments in EN3835-202.
Number of subjects (planned): Approximately 350
Study center(s): 15 sites in the United States
Diagnosis and inclusion/exclusion criteria:
Qualification for the Open-label Observation Phase of the Study
Inclusion criteria for observation:

 1. Voluntarily sign and date an informed consent agreement 2. Have participated in and completed the double-blind study EN3835-201 3. Be willing to apply sunscreen to any treated quadrant before each exposure to the sun while participating in the study (ie, screening through end of study)
Exclusion criteria for observation:
None
Qualification for the Open-label Treatment Phase of the Study
Inclusion criteria for treatment:

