7. LIST OF ABBREVIATIONS

The following abbreviations and specialist terms are used in this study protocol.

Table 5: Abbreviations and Specialist Terms

Abbreviation	Definition
AE	Adverse event
Assigned quadrant	Assigned quadrant (ie, left or right buttock, or the left or right posterolateral thigh) that was suitable for treatment and was randomly assigned in the double-blind study (EN3835-201). To be suitable for treatment the quadrant must have an Investigator CR-PCSS and subject PR-PCSS score of 3 or 4 and a Hexsel CSS score of no greater than 13 at Screening B visit and at Day 1 visit.
AUX-I	Clostridial class I collagenase
AUX-II	Clostridial class II collagenase
CFR	Code of Federal Regulations
CRF	Case report form
CR-PCSS	Clinician-Reported Photometric Cellulite Severity Scale
CSS	Cellulite Severity Scale
ECG	Electrocardiogram
eCRF	Electronic case report form
EDC	Electronic data capture
EFP	Edematous fibrosclerotic panniculopathy
FDA	Food and Drug Administration
GCP	Good clinical practice
HREC	Human research ethics committee
IB	Investigator Brochure
ICF	Informed consent form
ICH	International Conference on Harmonisation
IEC	Independent ethics committee
I-GAIS	Investigator Global Aesthetic Improvement Scale
IND	Investigational new drug
IRB	Institutional review board
ITT	Intent-to-treat
kDa	Kilodalton
MedDRA	Medical Dictionary for Regulatory Activities
mITT	Modified intent-to-treat
PCS	Potentially clinically significant
PR-PCSS	Patient-Reported Photometric Cellulite Severity Scale
Qualified designee	Qualified by education and training to perform the study procedure (eg, sub-Investigator, nurse)

Table 5: Abbreviations and Specialist Terms (Continued)

Abbreviation	Definition
SAE	Serious adverse event
SAP	Statistical Analysis Plan
Selected quadrant	Quadrant (ie, left or right buttock, or the left or right posterolateral thigh) that is suitable for treatment and is selected by patient and investigator for treatment. To be suitable for treatment the quadrant must have an Investigator CR-PCSS and subject PR-PCSS score of at least 3 or 4 and a Hexsel CSS score of no greater than 13 at Screening B visit.
S-GAIS	Subject Global Aesthetic Improvement Scale
TEAE	Treatment-emergent adverse event; adverse events that occur on or after the first injection of study drug

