11.2.1. Subject Inclusion Criteria for Treatment

To qualify for treatment in the study a subject must:

1. Voluntarily sign and date an informed consent agreement
2. Have participated in and completed the double-blind study EN3835-201
3. Be a female ≥ 18 years of age
4. At Screening B visit, have at least 1 quadrant with:
 - a. a score of 3 or 4 (moderate or severe) as reported by the subject (PR-PCSS), and
 - b. a score of 3 or 4 (moderate or severe) as reported by the Investigator (CR-PCSS), and
 - c. a Hexsel CSS score no greater than 13
5. Be willing to apply sunscreen to the selected treatment quadrant before each exposure to the sun while participating in the study (ie, Screening B through end of study)
6. Be judged to be in good health, based upon the results of a medical history, physical examination, and laboratory profile at Screening B

7. Have a negative urine pregnancy test at Screening B and before injection of study drug and be using an effective contraception method (eg, abstinence, intrauterine device [IUD], hormonal [estrogen/progestin] contraceptives, or double barrier method) for at least 1 menstrual cycle prior to study enrollment and for the duration of the study; or be menopausal defined as 12 months of amenorrhea in the absence of other biological or physiological causes, as determined by the Investigator; or post-menopausal for at least 1 year; or be surgically sterile
8. Be willing and able to cooperate with the requirements of the study
9. Be able to read, complete and understand the patient-reported outcomes rating instruments in English

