12.1.4.2. Treatment Session 1 (Treatment Visit 1)

Pre-injection

1. Confirm eligibility criteria (section 11)
2. Take digital photography of selected quadrant before dimple marking (section 13.1)
3. Record concomitant medications/procedures (section 12.2)
4. Vital sign measurements (section 14.8)

5. Collection of samples for:
 - a. anti-AUX-I and anti-AUX-II antibody testing (section 14.7.1)
 - b. urine pregnancy testing (section 14.7)
6. Select and mark dimples to be treated (section 12.1.4)
7. Take digital photograph of selected quadrant after dimple marking (section 13.1)

Injection

Administration of study drug in the prone position (see below)

[figure not shown]
Post-injection

1. Record number of dimples treated and number of injections administered
2. Vital sign measurements (section 14.8)
3. Injection site reactions and local tolerability
4. Adverse events (section 14)

The selected quadrant will be photographed before and after dimple marking while the subject is standing in a consistent relaxed pose as described in the Photography Manual. Before injection at treatment session 1, the Investigator or qualified designee will begin the session by selecting dimples within the chosen quadrant that are well defined, evident when the subject is standing, and suitable for treatment; treatment consists of up to 12 injections per session. Because the goal of treatment is to improve the aesthetic appearance of the entire quadrant, the Investigator will be instructed to select dimples that in his or her opinion would most improve the aesthetic appearance of the entire quadrant. The same dimples within a quadrant or different dimples within a quadrant may be treated at each session but injections must all be within the selected quadrant for all 3 sessions.

For each dimple selected for treatment, the Investigator or qualified designee will choose injection sites (injection sites within a dimple should be spaced approximately 2 cm apart, if a dimple requires more than 1 injection). Each injection site will be marked with a “dot” using a surgical marker. For round dimples, the “dot” will be placed in the center of the dimple; for elongated dimples, “dots” will be spaced out approximately 2 cm along the longer axis of the dimple. The Investigator or qualified designee will then use a surgical marker to circle each of the dimples selected for treatment. Circles in the selected quadrant should not overlap.

[figure not shown]
Examples of subject dimple marking:

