13.1.1.1. Patient-Reported Photonumeric Cellulite Severity Scale (PR-PCSS)

The PR-PCSS will be conducted for the purpose of assessing the severity of cellulite in the buttock or thigh; there are separate scales for buttocks or thighs. The scales are 5-level photonumeric scales developed specifically for patients and used by the subject to assess the severity of their cellulite in the quadrants by viewing digital images of each of their quadrants

captured by photography at the visit; the ratings range from 0 (None) to 4 (Severe) with labels and descriptors to aid the subject in the assessments.

All subjects who enter the observation-only phase of the study will have the PR-PCSS evaluation at months 3, 6, 9, and 12 (and at specified visits in [Table 4](#) for subjects originally treated with active in the double-blind study and being assessed for treatment durability beyond Day 360) or at the end of study visit.

For subjects electing re-treatment or re-dosing after the study drug blind is broken in study EN3835-201, a Screening B visit (Baseline) within 14 days before dosing Day 1 will occur. Subjects will have digital photographs taken of all 4 quadrants as done in the double-blind trial for qualifying purposes. Subjects will then perform the PR-PCSS for both buttocks ([Figure 1](#)) and thighs ([Figure 2](#)) and will be reminded of their proper use ([Appendix D](#)).

At the beginning of visits on Days 22, 43, and 71 digital photographs of the selected quadrant will be taken. If the buttock is the treated region, subjects will be given the PR-PCSS for the buttock to use to make their evaluation; if the thigh is the treated region, subjects will be given the PR-PCSS for the thigh to make their evaluation.

Figure 1: Patient-Reported Photonumeric Cellulite Severity Scale (PR-PCSS) for the Buttock

Patient Reported Photonumeric Cellulite Severity Scale (PR-PCSS) – Buttock

0 None

No evident cellulite

1 Almost None

A few superficial dimples or ridges

2 Mild

Several dimples or ridges of which most are superficial

3 Moderate

Many dimples or ridges of which most are somewhat deep

4 Severe

A lot of dimples or ridges of which many are deep covering most of the skin area

Produced by CANFIELD Scientific, Inc.

Version 8.0

© 2015 Endo Pharmaceuticals
Confidential – Not to be distributed

Figure 2: Patient-Reported Photonumeric Cellulite Severity Scale (PR-PCSS) for the Thigh

Patient Reported Photonumeric Cellulite Severity Scale (PR-PCSS) – Thigh

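### For quadrants treated in EN3835-202, the Screening B rating that must be 3 or 4 to qualify is also the baseline, so regression to the mean inflates open-label response, chiefly the 1-level and single-scale rates

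*Combined protocol and SAP*

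**What the plan says.** All references are to the current protocol (Amendment 4).

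- **Gate.** Section 11.2.1, criterion 4, requires at Screening B a quadrant with "a score of 3 or 4 (moderate or severe) as reported by the subject (PR-PCSS), and" and "a score of 3 or 4 (moderate or severe) as reported by the Investigator (CR-PCSS), and" a Hexsel CSS of at most 13. If several quadrants pass, the subject chooses (12.1.4).
- **Baseline.** Section 12.1.4 takes the ratings made "during the open-label Screening B visit will be the baseline severity of EFP in the selected quadrant". Section 13.1.1.1 agrees: "a Screening B visit (Baseline) within 14 days before dosing Day 1 will occur". The synopsis and section 13.1.1.4 also label Screening B as baseline, and 17.5 labels the screening rating so.
- **No Day 1 rating.** The synopsis plans visits "for cellulite severity assessments at Screening visit and on Days 22, 43, and 71", and Table 3 has no PR-PCSS or CR-PCSS at Treatment Visit 1. Section 12.1.4.2 does include "Take digital photography of selected quadrant before dimple marking" at that visit.
- **Parent study.** For EN3835-201, section 12.1.4 states "Baseline is Day 1 of study EN3835-201". The definition of the assigned quadrant in section 7 requires 3 or 4 on both PCSS scales and "a Hexsel CSS score of no greater than 13 at Screening B visit and at Day 1 visit".
- **Use of baseline.** Response is an improvement of at least 2 (or 1) levels from baseline on both scales (17.5.1). The same comparison governs entry to the open-label durability population (17.2.4.2), and recurrence is return to baseline on both scales (17.5.2). Section 8.6 acknowledges that efficacy here is uncontrolled.

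**The concern.** One rating does two jobs. Unless ratings repeat perfectly, quadrants admitted because they scored 3 or 4 include some that scored high by chance. At the next rating these drift back, and the drop is counted as improvement. Two features work in the same direction: four quadrants are screened, and a quadrant treated with EN3835 in EN3835-201 must score at or above its EN3835-201 baseline on both scales to be re-treated.

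At stake is the secondary objective on severity in quadrants treated in this study. Chance responders raise the responder proportions and enter the open-label durability population. A baseline that is too high also makes return to baseline harder to reach, so recurrence may be understated. With no control arm, nothing in the descriptive summaries would show this.

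**Working it through.** The plan gives no figure on this point: no rating reliability, no expected response rate, and a sample size of about 350 without inputs. There is nothing to reproduce, so the check is a calculation under stated assumptions.

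**Assumptions (not from the documents).** True severity T is normal with mean 2.5 or 3.0 and is shared by both raters. Total SD is 0.8 or 1.0, and test-retest ICC is 0.6, 0.7, 0.8 or 0.9. That makes 16 scenarios. Each rating is T plus independent error with variance (1 − ICC) × SD², rounded to 0–4.

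**Formulas.** Given T, let p_s be the probability of rating s, and F_s the probability that the follow-up rating is s or less. Then:

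- h = p_3 + p_4 (passes the gate)
- g = p_3·F_2 + p_4·F_3 (passes, then falls at least 1 level)
- k = Σ p_s·F_(s−1), s = 1 to 4 (falls at least 1 level from an ungated rating)

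The two raters are independent given T, so the composite rates are as follows, with E the mean over T:

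- **A**, current rule (Screening B is gate and baseline): E[g²] / E[h²]
- **B**, EN3835-201 rule (3 or 4 at Screening B and at Day 1; Day 1 is baseline): E[(hg)²] / E[h⁴]
- **C**, gate at Screening B, separate ungated Day 1 baseline: E[(hk)²] / E[h²]

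For 2 levels, F_(s−2) replaces F_(s−1). For a true improvement d, F is taken at T − d.

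**One scenario in full** (mean 2.5, SD 1.0, ICC 0.6, no true change): A = 5.32% / 35.24% = 15.1%; B = 2.48% / 23.34% = 10.6%; C = 2.64% / 35.24% = 7.5%. At the other end (mean 3.0, SD 0.8, ICC 0.9) the rates are 3.1%, 2.3% and 2.1%.

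**Ranges over the 16 scenarios** (%, or points for differences, which are taken within scenario):

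| True change, endpoint | A | B | C | A − C | A − B |
|---|---|---|---|---|---|
| none, ≥1 level | 3.1–15.1 | 2.3–10.6 | 2.1–7.5 | 1.1–7.6 | 0.9–4.5 |
| none, ≥2 levels | 0–0.6 | 0–0.3 | 0–0.2 | 0–0.4 | 0–0.3 |
| 0.5 level, ≥1 level | 27.3–41.3 | 23.4–33.7 | 20.7–27.9 | 5.7–16.8 | 3.7–7.5 |
| 1 level, ≥1 level | 57.5–84.1 | 52.4–81.7 | 45.3–74.4 | 5.9–19.8 | 1.9–6.7 |
| 1 level, ≥2 levels | 3.1–15.1 | 2.3–10.6 | 2.1–7.5 | 1.1–7.6 | 0.9–4.5 |

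The last row repeats the first because F_(s−2) at T − 1 equals F_(s−1) at T. A Monte Carlo run of the same model agreed to within about 0.2 points.

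**Single scale, ≥1 level, no true change:** E[hg] / E[h²] = 13.5–36.2% under A, against E[h²k] / E[h²] = 11.9–26.8% under C.

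**Variant.** Here the raters' true severities correlate at 0.7, SD is 0.8, and the treated quadrant is picked from the qualifying ones out of four, at random or as the worst self-rated. With no true change the 1-level composite is 2.4–14.4% under A, 1.5–9.6% under B and 1.4–6.3% under C. The excess of A over B is about 0.7–5.3 points. PR-PCSS alone gives 14–39% under A and 11–25% under C.

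**Day 1 ratings below 3.** The share of selected quadrants that would rate below 3 on at least one scale on Day 1 is 1 − E[h⁴] / E[h²] = 8–34% (6–39% in the variant).

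**The case against.** The stakes are limited. Safety is the primary objective (9.1), section 13.1 puts the emphasis there, and efficacy is descriptive, so no type I error or power is affected. The size rests wholly on assumed reliability. With no true change the 2-level composite is nearly untouched. All of this stands, and it bounds the point without removing it.

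Three stronger readings are tempting, and the documents do not support them.

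- **That EN3835-201 had a clean baseline and open-label results are on a wholly different footing.** Its Day 1 rating also had to be 3 or 4, after a first qualifying visit. The fair comparison is A with B, not A with C, and the difference is one of degree. What EN3835-201 had in addition was a placebo arm.
- **That every EN3835-202 result is affected and the durability data are simply pooled.** Observation-only quadrants, and quadrants treated with EN3835 only in the double-blind study, refer to the EN3835-201 baseline. Sections 17.2.4.1 and 17.2.4.2 define separate durability populations, and 17.2 keeps efficacy analyses within cohort. Only the Overall Durability Population (17.2.4) mixes the two baselines.
- **That a subject's wish for treatment pushes her own score up.** This is possible, but nothing in the documents measures it. She rates in private, and the investigator must independently give 3 or 4 without knowledge of her rating. No such effect is included in the figures above.

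Timing is a fair practical objection. Amendment 4 is dated October 2, 2017. If the estimated last completion of June 2018 holds and each open-label quadrant is followed for 12 months, first injections would fall by about June 2017. A Day 1 rating introduced now would then reach few courses.

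**Conclusion.** The point holds for quadrants treated in EN3835-202. Gate and baseline are the same rating, no Day 1 PCSS rating exists, and no analysis removes the resulting bias. The direction is certain if ratings are not perfectly repeatable; the size is not known.

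With ICC 0.6–0.9 and no true change, the 1-level composite is about 2–15%, against about 1.5–7.5% from an ungated Day 1 rating. The excess over the EN3835-201 rule is about 1–5 points. The 2-level composite is 0.6% or less with no true change, but gains about 1 to 7.6 points over an ungated baseline if there is a true 1-level improvement. The effect on recurrence was not quantified.

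This is a worthwhile and inexpensive correction to a secondary, descriptive result. It does not touch the safety objective.

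**What to change.** **For new courses.** At Treatment Visit 1, before dimple marking, obtain PR-PCSS from the pre-marking photograph already taken, then CR-PCSS, for the selected quadrant. Use these as the analysis baseline for open-label response, durability entry and recurrence. Treatment Visits 2 and 3 already follow this sequence. Leave eligibility where criterion 4 puts it, at Screening B, and state that a Day 1 rating below 3 leaves eligibility as it is and is analysed as observed. Without that statement, the eligibility confirmation at Treatment Visit 1 could be read as a second gate.

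**Text to amend together.** Table 3, 12.1.4, 12.1.4.2, 13.1.1.1, 13.1.1.4, 17.5 and the synopsis; otherwise the baseline statements will contradict each other. The sentence in 12.1.4 also covers the Hexsel CSS, which can stay on Screening B if the text says so.

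**For courses already started.** Keep Screening B as baseline, report these courses separately from any with a Day 1 baseline, and state the upward bias beside the responder rates. Present double-blind and open-label durability separately rather than relying on the Overall Durability Population. Where the same quadrant was rated before Screening B, add a sensitivity analysis from that rating.

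**Cost.** A few minutes per course, with no new visit or photograph; somewhat lower reported response rates; and two baseline definitions if the change comes mid-study.
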